#### **3.5.1.2 *Exclusion Criteria***

Patients will be excluded from the study if they have a documented history of moderate to severe traumatic brain injury. If they have a prior history of other neurological (i.e. Epilepsy, MS, Alzheimer's Disease), psychiatric (i.e. Psychotic disorder or other history of a mental health disorder) or substance abuse disorders. Subjects will be excluded if they have no fixed address or are incarcerated, as that would hinder follow up. The St. Michael's Hospital Head Injury Clinic Steering Committee and the St. Michael's Hospital Research Ethics Board will be required to approve the study.

### **3.5.2 Interventions**

#### **3.5.2.1 *Educational Intervention***

Participants in the education arm of the study will be provided with three PowerPoint presentations. Material for these slides has been adapted from material developed by the Ontario Neurotrauma Foundation. Topics to be addressed will surround post-traumatic headache and will include information regarding common symptoms, timeline for improvement, red- flags and when to seek medical attention. The first session is conducted in-person to provide participants with an outline of the study and to discuss the first PowerPoint session. For the remainder of the sessions, the PowerPoint slides will be emailed with follow up telephone or in person discussions with patients to ensure that they received the material, understood it and could open it. At the 12-week time point (post study enrollment) we will also ensure that patients have filled out the survey's via REDCap and perform an Exit interview. If patients return to the clinic for subsequent follow up visits, we will attempt to provide the session at the follow up visit that closely relates to the time point stated above.

For those patients not allotted to the education arm, at the end of the study they will be offered the educational material should they wish to review it.

**3.5.2.2 Summary of education by session: PowerPoint slides will be split into three distinct sections.**

*Initial session: (0 weeks): (In person)* We will outline the study. Approximately 30 minutes in duration.

[figure not shown]
- Review inclusion/exclusion criteria
- Explain study goals
- Obtain written/verbal informed consent
- We will cover topics such as defining the basic anatomy and the consequences of head trauma. We will include common symptoms along with when to seek medical guidance, medications to avoid and helpful lifestyle and treatment tips. Patients will be provided with links to approved websites.
- Prior to this session
  - Complete demographic information, medical history, trauma history and participant contact information (email or phone) will be gathered. If patients are identified in the ER, this information will be provided by the Triage nurse and forwarded to the research assistant who will be responsible for follow-up and providing the study materials.
  - Rivermead Post-Concussive Questionnaire (RPCSQ), PART-O and QOLIBRI (Yellow form: See Appendix) will be completed.
- *Second Session (6 weeks): (via email)*. Explain importance of keeping brain active; define the assessment of brain activity. 10-20 minutes to review the PowerPoint. Follow up will be done 1 week later either in person, email or via telephone to ensure patients are able to open the PowerPoint and have reviewed the literature. There will be no education or discussion about current treatment regimen or symptoms. Should a patient have questions regarding their current treatment plan or symptoms, our volunteers will put patients in contact with the Head Injury Nurse. All calls will be made during clinic hours in order to help facilitate communication with the clinic.

*Third Session (12 weeks)- (In person or sent via email)* We will explain importance of stress, sleep, and exercise on brain function, define the influence of lifestyle on recovery.

Approximate duration is 10-20 minutes. 1 week later follow up via telephone or email will occur by the methods listed above to ensure that the patient was able to open the PowerPoint. At this time we will:

- Re-verify inclusion criteria to be done by Research Assistant. There will be no education or discussion about current treatment regimen or symptoms. Should a patient have questions regarding their current treatment plan or symptoms all calls will be made when the Head Injury Nurse is available to connect with patients directly.

- Rivermead Post-Concussive Questionnaire (RPCSQ), PART-O and QUOLIBRI will be completed via telephone or email and entered via REDCap into our database. Survey data will be uploaded by student or research assistant that is unaware of the patient's randomization.
- The patients who did not participate in the education seminar will fill out surveys at week 0 and 12.

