#### **3.3.3 Secondary Objectives**

##### **3.3.3.1 Key Secondary Objectives**

When and what type of health care services do participants in this study access, how frequently and is there a difference and between the two groups.

[figure not shown]

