#### **3.5.5 Secondary Outcome Measures**

For the secondary endpoints, we will analyze the frequency and type of health care patients accessed outside of their current standard of care during the 12-week study period. This will be compared to our controls and will include emergency room, family physician visits, hospital admissions and telehealth that are related to post traumatic headache symptoms.

Another end point we are interested in exploring is whether patients that are provided targeted headache education along with tertiary care has an increased frequency of social interactions in comparison to patients receiving the current standard of care. We are very interested in the hours that each patient devotes to their previous work or hobbies and we will be comparing this once again to patients in the clinic who are receiving the standard of care. This outcome will be measured using the PART-0 tool which asks questions about the type and frequency of social engagements that patients may encounter each week along with the hours that patients devote to returning back to work, school or homemaking.

Lastly, we are interested in whether or not education and reassurance alter a patient's perceived quality of life after a mild-traumatic brain injury. This will be analyzed by using the QOLIBRI (Quality of Life after Brain Injury). Using this scale we hope to capture whether or not patients believe they play an active role in their health and whether or not they feel empowered to alter their health status. It will hopefully also allow us to capture what

barriers there are to a patient's recovery in regard to what negative feelings and limits they perceive; preventing them from making a meaningful recovery.

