#### *Access to Medical Services*

Tracking patient's utilization of health care services during the time of the study is an important outcome that this study hopes to measure. The aim is to see if education can ultimately reduce unnecessary access to medical care. As stated previously we hope to accomplish this by providing information to patients on red flags and when to seek medical advice. Patients will be asked to recall the number of times they have sought out medical attention since they were last seen in the subspecialty clinic. This includes walk-in clinics, hospitals, their family MD, telehealth and ER visits. Future goals after this study has been completed would be to use the ICES database to quantify the utilization of health care services in this subset patient population.

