## **3.9 Appendices**

1. Consent to Participate in a Research Study
2. Yellow Baseline Questionnaire: Includes Rivermead, PART-O and QUOLIBRI
3. Blue follow up Survey: Included Rivermead Post Concussion Symptoms Questionnaire (RPCSQ), PART-O and the QUOLIBRI
4. Post Concussion Headache Assessment
5. Control and Study Participant Master Lists

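### Health-care use, the key secondary outcome, is defined over 12 weeks but collected by recall since the last clinic visit, with no form or study week named

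*Protocol*

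**What the plan says.** Protocol section 3.3.3.1 has one objective, which also asks for a comparison of the arms: "When and what type of health care services do participants in this study access, how frequently". Section 3.5.5 sets the outcome as "frequency and type of health care patients accessed outside of their current standard of care during the 12-week study period", to be compared with controls.

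Collection is described once, in section 3.7.4 under Access to Medical Services. Patients are to "recall the number of times they have sought out medical attention since they were last seen in the subspecialty clinic". No form, study week or visit is given there.

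Survey content is listed in several places, each time as the RPQ, PART-O and QOLIBRI:

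- Section 3.5.2.2, week 0: "Rivermead Post-Concussive Questionnaire (RPCSQ), PART-O and QOLIBRI (Yellow form: See Appendix) will be completed". The week-12 list in the same section names the same three instruments.
- Section 3.8.1 names those three and a demographic questionnaire.
- Section 3.9 lists the baseline form with the same three, and the follow-up form as "Blue follow up Survey: Included Rivermead Post Concussion Symptoms Questionnaire (RPCSQ), PART-O and the QUOLIBRI".

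On timing, section 3.5.2.2 states: "The patients who did not participate in the education seminar will fill out surveys at week 0 and 12". Section 3.7.1 adds that the standard-of-care arm gets the same questions and surveys as the education arm at those two times.

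**The concern.** The outcome definition and the collection rule describe different quantities. Section 3.5.5 needs a count over 12 weeks for every patient. Section 3.7.4 yields a count over whatever time has passed since that patient's last clinic visit. A patient seen recently reports a short period, and one not seen since enrolment reports the whole of it. Counts over unequal, unrecorded periods cannot be read as frequency during the study.

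The missing form and week make this harder to repair. If staff follow the survey lists as written, the item is not on either survey, and nothing else says when it is asked. Which form carries an outcome, when it is asked and over what period are matters of data collection. A later analysis plan cannot recover contacts that nobody asked about. The same holds for a week-0 count of earlier use, which is a natural predictor of later use and is not scheduled in the text.

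**Working it through.** The protocol states no figure for this outcome, so there is none to reproduce. The check is mainly a comparison of text, with two illustrations.

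**1. Definition against collection rule**

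| | Section 3.5.5 | Section 3.7.4, Access to Medical Services |
|---|---|---|
| Start of window | Start of the study period | Last subspecialty clinic visit |
| Length | 12 weeks, same for all | Varies by patient |
| Form or week | Not stated | Not stated |

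The two agree only for a patient who was seen in the clinic at enrolment, has not been seen there since, and is asked at week 12. If the last clinic visit came before enrolment, the recall also takes in contacts from before the study.

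**2. Share of the outcome window covered**

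Share = (weeks from last clinic visit to the question) / 12, with the question put at week 12. The gaps are assumptions, because the protocol gives no clinic return schedule.

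- 4 weeks: 4/12 = 33%
- 6 weeks: 6/12 = 50%
- 8 weeks: 8/12 = 67%
- 12 weeks: 12/12 = 100%

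Take patients who all have the same true rate of 4 contacts per 12 weeks (also assumed). The expected reported counts are 4 × 4/12 = 1.3, 4 × 6/12 = 2.0, 4 × 8/12 = 2.7 and 4 × 12/12 = 4.0. Patients with identical use can thus differ threefold in what they report.

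**3. Other possible sources of the item**

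- Section 3.8.1: demographic questionnaire and medical-record extraction. Service use is not mentioned.
- Section 3.6.2: an assessor template covering both groups. Its content is not given.
- Section 3.5.2.1: an exit interview at 12 weeks, described under the educational intervention. Its content is not given.
- Section 3.9: a headache assessment form, listed by title only.

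None is said to record health-care use.

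**4. What a week-0 count could add**

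Inputs: 28 per arm (section 3.5.6, before the attrition allowance). The rest is assumed: the education arm has half the control contact rate; the control mean is 2 or 4 contacts per 12 weeks; gamma between-patient variation has variance 0.5 or 1.0; the correlation between a patient's underlying rates in the two periods is 0.5 or 0.8. A log-linear model with robust standard errors was fitted with and without log(week-0 count + 0.5), using 1,500 replicates per scenario.

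| Mean | Variance | Correlation | Cut in variance of log rate ratio | Power without | Power with |
|---|---|---|---|---|---|
| 2 | 0.5 | 0.5 | 1% | 0.65 | 0.66 |
| 2 | 0.5 | 0.8 | 8% | 0.67 | 0.72 |
| 2 | 1.0 | 0.5 | 4% | 0.52 | 0.55 |
| 2 | 1.0 | 0.8 | 20% | 0.54 | 0.64 |
| 4 | 0.5 | 0.5 | 4% | 0.80 | 0.83 |
| 4 | 0.5 | 0.8 | 20% | 0.81 | 0.89 |
| 4 | 1.0 | 0.5 | 10% | 0.62 | 0.68 |
| 4 | 1.0 | 0.8 | 31% | 0.63 | 0.78 |

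The median variance cut is (8 + 10)/2 = 9%, and the median power gain is (5 + 6)/2 = 5.5 points. Rejection under the null was 0.055 to 0.09 for both analyses, so the power figures are somewhat generous. They serve to compare the two analyses, not as absolute values.

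**The case against.** The strongest reply is that absence is being inferred from forms that are not shown. The flow diagram and the figure comparing the arms are missing too. Section 3.9 says what the baseline form includes, which need not be a full list, and a short recall item would not usually be named beside validated instruments. Section 3.7.4 does commit to asking the question. This stands as a limit: the text supports no more than that the item is absent from the survey content as listed. It does not remove the mismatch between sections 3.5.5 and 3.7.4, which is in the protocol's own words.

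A reader might infer that controls have no route for this outcome, or that the education arm would be asked at its extra contacts and controls would not. The documents do not support either reading. Controls also have the questionnaire and record extraction of section 3.8.1. Section 3.7.1 promises both arms the same questions at weeks 0 and 12. The follow-up after the second session (section 3.5.2.2) is for checking that the material opened and was reviewed, and section 3.6.2 limits the difference between groups to that kind of check. No section ties any education-arm contact to this outcome. Nor does the protocol suggest that clinic visits will be timed differently by arm: section 3.5.2.5 gives both arms the same standard of care.

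On the covariate, it is fair to say that a randomised comparison does not need one and that covariate choice is often left to an analysis plan. Patients enter at least 12 weeks after injury, some through the emergency room (section 3.5.7), so prior use may partly reflect the injury or the referral and predict later use less well. These points stand. They make the covariate an optional improvement, not a correction.

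**Conclusion.** The point holds as a mismatch between outcome definition and collection rule, with no form or study week stated. It applies to both arms. Followed as written, section 3.7.4 gives counts over unequal periods that need not match the 12 weeks of section 3.5.5. Coverage is 33% to 67% if the last clinic visit was 4 to 8 weeks before the question, and that spacing is an assumption. The effect is a mismeasured and noisier key secondary outcome. The documents give no ground for claiming bias between the arms.

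The lack of a scheduled week-0 count is secondary and concerns precision only. The range of 1% to 31% lower variance rests wholly on assumed inputs, and the largest gains need a correlation of 0.8.

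The change is worth making because it is cheap. If the forms already carry the item with a fixed window, the sponsor need only say so and correct section 3.7.4.

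**What to change.** - In section 3.7.4, replace recall since the last clinic visit with a fixed window that matches section 3.5.5: the period since enrolment, asked at week 12, with the enrolment date printed on the form.
- Put the same items, by type of service, on the week-12 (Blue) survey in both arms, and name them wherever its content is listed (sections 3.5.2.2, 3.8.1 and 3.9). Use one list of services throughout; walk-in clinics now appear in section 3.7.4 but not in section 3.5.5.
- Take the outcome only from that survey, not from other contacts.
- As an addition, ask the same items for a fixed prior period, such as the previous 12 weeks, on the week-0 (Yellow) survey in both arms, and use that count as a covariate in the between-arm comparison.

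The cost is one recall block on two existing surveys, a few minutes per patient, and one model term. The week-0 block can be dropped without affecting the validity of the comparison; the fixed window on the week-12 survey should not be.

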### **3.3 Study Hypothesis and Objectives**

#### **3.3.1 Hypothesis**

Providing targeted education headache education to patients who have suffered from mild traumatic brain injury will reduce symptom scoring on the Rivermead Concussion Questionnaire by week 12 of the study.

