### **3.7 Methods: Data collection, management and analysis**

#### **3.7.1 Data Collection**

For all visits each patient will fill out a questionnaire (See Appendices for full surveys) using RedCap. If a patient is unable to enter the data using email directly, one of our research assistants will enter the data into the RedCap system via telephone interview. For the follow up survey if there is no response, we will attempt to contact the patient by phone three times. In regard to those patients seen in follow up in the clinic, we will ensure that they finish their follow up questionnaires after being seen by a healthcare professional to avoid unblinding. Patients' receiving the standard of care will be asked the same questions at week 0 and 12 with the same surveys as the education intervention arm of the study. A secure password protected master linking log will be able to house the patient name with study identification number.

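### The protocol contradicts itself on when the education arm's final outcomes are collected (week 12 or week 13), and at week 12 the third session has had no time to act

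*Protocol*

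**What the plan says.** **Endpoint.** The hypothesis (section 3.3.1) is that targeted education "will reduce symptom scoring on the Rivermead Concussion Questionnaire by week 12 of the study". Section 3.3.3.2 sets the PART-O objective at 12 weeks, and section 3.5.5 counts health-care use over a 12-week period.

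**Education arm, first statement.** Section 3.5.2.1 says: "At the 12-week time point (post study enrollment) we will also ensure that patients have filled out the survey's via REDCap". An exit interview is placed at the same point.

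**Education arm, second statement.** Section 3.5.2.2 heads the last session "Third Session (12 weeks)- (In person or sent via email". It then says "1 week later follow up via telephone or email will occur by the methods listed above", and the sentence runs on "to ensure that the patient was able to open the PowerPoint. At this time we will". The list that follows includes: "Rivermead Post-Concussive Questionnaire (RPCSQ), PART-O and QUOLIBRI will be completed via telephone or email and entered via REDCap into our database".

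**Control arm.** Section 3.5.2.2 states: "The patients who did not participate in the education seminar will fill out surveys at week 0 and 12". Section 3.7.1 repeats it: "Patients' receiving the standard of care will be asked the same questions at week 0 and 12".

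**The concern.** The primary comparison is between arms at a stated time. Two things have to be fixed for it to be interpretable: both arms must be measured at the same time from randomisation, and it must be clear how much of the intervention came before the measurement. The protocol leaves both open for the education arm.

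If sites follow the more literal reading of section 3.5.2.2, the education arm is surveyed a week later than controls, and time since randomisation is confounded with allocation. The bias need not run the same way for every outcome. An extra week for any improvement would favour education on the RPQ, while a longer recall period would tend to raise that arm's visit count.

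If sites follow section 3.5.2.1, timing is equal, but the session on stress, sleep, exercise and lifestyle is dated to the week in which its effect is to be measured. A finding for the three-session programme would then be credited to material that had no time to work. This bears most directly on the PART-O objective, which asks about reinforcement of lifestyle and treatment strategies at that same time.

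**Working it through.** The protocol states no figure for this point, so the check is a timetable built from its own dates.

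**Inputs**
- Sessions at weeks 0, 6 and 12 (section 3.5.2.2).
- Follow-up one week after session three (section 3.5.2.2).
- Control surveys at weeks 0 and 12 (sections 3.5.2.2 and 3.7.1).
- Endpoint by week 12 (section 3.3.1).
- Surveys at 12 weeks after enrolment (section 3.5.2.1).

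**Step 1: what one week later means.** Session two is dated week 6, and section 3.8.1 puts its follow-up at 7 weeks, so the protocol counts session week + 1. For session three this gives 12 + 1 = week 13.

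**Step 2: weeks available to each session before the survey.** Formula: survey week minus session week.

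| Reading | Education survey | Control survey | Session 1 | Session 2 | Session 3 | Gap between arms |
|---|---|---|---|---|---|---|
| Section 3.5.2.2, literal | 13 | 12 | 13 − 0 = 13 | 13 − 6 = 7 | 13 − 12 = 1 | 1 week |
| Section 3.5.2.1 | 12 | 12 | 12 − 0 = 12 | 12 − 6 = 6 | 12 − 12 = 0 | 0 weeks |

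On the first reading session three has one week to act, but the education arm is then measured after the week-12 endpoint. On the second reading timing is equal and session three has none.

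**Step 3: recall of health-care use.** Section 3.7.4 relies on patient recall since the last visit to the subspecialty clinic. If that visit is the enrolment visit and recall runs to the survey date (both assumptions), the windows on the first reading are 13 and 12 weeks. The ratio is 13/12 = 1.083, about 8% longer in the education arm. Patients with a later clinic visit would have a different window.

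**Step 4: does another passage resolve it?** Section 3.5.2.1 lets a session move to a nearby clinic visit, so some patients may receive session three early. Nothing requires it to precede the survey.

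**The case against.** The strongest reply is that unequal timing is not established, and that part stands. Section 3.5.2.1 is the only place that attaches an explicit week to the education arm's final survey, and it says 12. Week 13 is never written. The phrase introducing the task list could refer to the session rather than its follow-up, and the list also holds the control-arm item dated weeks 0 and 12, so it is not purely a list for a week-13 contact. The flow diagram and the arm-by-arm figure are not shown and may settle the matter. A reader might infer that the arms will certainly be measured a week apart; the documents support only a contradiction in which that is one of two outcomes.

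A reader might also want to put a size on it. Two calculations are tempting, and neither is supported.
- **Lost power.** With 28 per arm, 80% power corresponds to 0.762 SD. Removing one third, one sixth or one tenth of that effect leaves about 46%, 65% or 71% power. But 0.762 SD is solved back from the sample size. Section 3.5.6 uses headache proportions, and the protocol states no SD. The share owed to session three is also unknown. By stated minutes it is 10/(30 + 20 + 10) = 17% to 20/(30 + 10 + 20) = 33%, and part of the first 30 minutes goes to consent and study explanation. The range is illustrative only, and applies only if the survey is at week 12.
- **One week of recovery.** Spreading the target reductions evenly over 12 weeks gives 3/12 = 0.25 points on RPQ-3 and 10/12 = 0.83 on RPQ-13. This treats the target effect as spontaneous recovery. Patients are enrolled at least 12 weeks after injury (section 3.5.7), and section 3.1 cites persistently high RPQ scores despite treatment, so the figures probably sit at the upper end.

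It can also be said that a last session at study end is the investigators' choice and does not invalidate a randomised comparison of what was delivered by week 12. That is right. It limits what may be concluded, not the validity of the comparison. Nor is it an error to survey patients in the same contact that checks the material: section 3.6.2 plans a template to keep contacts alike, and separating them is a preference that might add a contact.

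**Conclusion.** The concern holds as an internal contradiction with a consequence on either side. Sections 3.5.2.1 and 3.5.2.2 do not agree on the education arm's final survey date. On the more literal reading of section 3.5.2.2, the arms are surveyed one week apart, and recall windows may be 13 against 12 weeks under the assumptions stated above. On the section 3.5.2.1 reading, session three has 0 weeks before the endpoint, so the week-12 result is about sessions one and two. What is certain is the timetable arithmetic and that, as dated, session three cannot contribute to an outcome by week 12. The effect on RPQ scores or power cannot be derived from the protocol.

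**What to change.** Reconcile sections 3.3.1, 3.5.2.1, 3.5.2.2 and 3.7.1:

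1. Set one outcome-survey date for RPQ, PART-O, QOLIBRI and health-care use, counted from randomisation and identical in both arms.
2. State which education sessions precede that date, and word the hypothesis and conclusion so that they cover only the education delivered before it.

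Which week is used and when the sessions are given is for the investigators to decide; the passages only have to agree. The cost is protocol wording, REDCap survey dates and possibly a narrower conclusion about the three-session programme. If follow-up data already exist, the date of each survey and of session three should be reported by arm, so that readers can see which schedule was followed.
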